# Part I : Trial related part of the protocol

# 1 Title of the trial

Local injection of collagenase clostridium histolyticum (XiapexR) for refractory gastrointestinal strictures: an open-label pilot study.

### 2 Trial number

Protocol:AGO/2018/004

EudraCT number: 2018-003637-14

# 3 Objective of the study

To investigate whether intralaesional injection with collagenase clostridium histolyticum (XiapexR) into the stricture followed by dilation 24 hours later improves the outcome of patients with refractory gastrointestinal strictures as compared to dilation alone (standard of care).

# 4 End point(s) and timepoint(s) of evaluation

### Primary outcome measure:

Number of repeat dilations that are required over a timespan of 6 months.

### Secondary outcome measures:

1) time to first repeat dilation

- 2) complication rate.
- 3) For upper gastrointestinal strictures only: Dysphagia/gastric outlet obstruction

score (0:, able to eat normal diet; 1: moderate passage: able to eat some solid foods;

2: poor passage: able to eat semi-solid foods only; 3: very poor passage: able to drink liquids only; 4: no oral intake possible

4) For lower gastrointestinal strictures only: (Ileo)colorectal obstruction scoring system (0, requiring continuous decompression; 1, no oral intake; 2, liquid or enteral nutrition; 3, oral intake of soft solids, low-residue diet, or full diet with symptoms of stricture\*; and 4, oral intake of soft solids, low-residue diet, or full diet without symptoms of stricture\*. Symptoms of stricture include abdominal pain/cramps, abdominal distension, nausea, vomiting, constipation, and diarrhea which are related to gastrointestinal transit).

## 5.2 Sponsor

Ghent University Hospital, with a grant of the Belgian Society of Gastrointestinal Endoscopy.

# 6 Introduction

The main causes of benign gastrointestinal (GI) strictures are inflammatory (eg: reflux disease, eosinophilic esophagitis, Crohn's disease, caustic...) or iatrogenic (postirradiation, post endoscopic (sub)mucosal resection, post radiofrequency ablation, anastomotic...). Most strictures respond well to endoscopic balloon dilation. Nonetheless, more than one third of patients develop recurrent symptoms after dilation within the first year (1).

In some case, the stricture can be difficult to treat and require multiple dilation sessions to obtain long-term relief of dysphagia, eating difficulties or lower GI obstructive symptoms (2, 3). A refractory stricture is defined as a cicatricial or fibrotic narrowing luminal diameter resulting in clinical symptoms of a) dysphagia (esophageal strictures), b) gastric outlet obstruction (for strictures of the stomach, pylorus, duodenum of gastrojejunal anastomosis) or c) lower GI obstruction (abdominal distension and cramps, vomiting) with an inability to successfully remediate the anatomic problem to a sufficient diameter over 3 dilation sessions at two-week intervals (4). A recurrent stricture is defined as a cicatricial or fibrotic narrowing with an inability to maintain a satisfactory luminal diameter for four weeks (4). Several options (stenting, intralesional injection of corticosteroids, needle knife incision) have been proposed to manage these strictures, with a varying success rate (5). A significant proportion of patients will finally need self-bougienage or surgery (5).

In conclusion, the treatment of GI strictures remains a challenge for clinicians and there is an unmet need for novel approaches to manage the patients suffering from this condition in order to avoid repeated dilations and/or invasive surgery.

XiapexR is a locally injectable collagenase approved for the management of Dupuytren's and Peyronie's disease (6, 7). Xiapex is a mixture of two collagenases, enzymes produced by the bacterium *Clostridium histolyticum* that dismantle collagen. Approximately 24 hours after local injection, the collagen fibres have lost their

strength and can be easily broken by manipulation. This therapy has been a breakthrough in the management of Dupuytren's disease, avoiding surgery in the vast majority of patients (6).

After local injection, the collagenases do not reach the bloodstream in significant amounts and are presumed to largely stay at the point of injection until they are broken down by proteases. As a result, side effects are uncommon and are most often injection site reactions including lymphadenopathy (swollen lymph nodes), itching, pain, oedema, and bleeding (for example in the form of bruises or ecchymoses). Allergic reactions are seen in less than 1% of patients (8).

XiapexR has been proposed as a promising treatment for refractory urethral strictures but has never been evaluated in refractory GI strictures (9).

# 7 The present study

## 7.1 Study design

Proof of concept open pilot study with a historical control cohort.

## 7.2 Medication

## 7.2.1 Composition and dosing

One vial (0.9mg) xiapex in 3ml dissolvent (also provided by the company) will be divided over 4 quadrants within the fibrotic stricture

## 7.2.2 Producer

Lonza AG [name] Switzerland

## 7.2.3 Distributor

Swedish Orphan Biovitrum AB [name]

Sweden

## 7.2.4 Packaging

Xiapex powder is supplied in a clear glass vial (3 ml, type I glass) with rubber stopper, aluminium seal and flip-off cap (polypropylene). Solvent: 3 ml solution supplied in a clear glass vial (5 ml, type I glass) with rubber stopper, aluminium seal and flip-off cap (polypropylene).

## 7.2.5 Administration way

Intralaesional injection.

## 7.2.6 Labelling

Xiapex is a commercialized product and the commercially available labelling will be used. A study label will be applied to the medication (not obscuring the original label), with following information:

Xiapex 0,9 mg poeder en 3 ml oplosmiddel voor oplossing voor injectie	
EudraCT N°: 2018-003637-14	
TRIAL subject ID nr: Initialen: Datum/ Date visite:	
ENKEL VOOR STUDIEGEBRUIK Gebruiksaanwijzing: Eén vial (0.9mg) xiapex in 3 ml oplosmiddel intralaesioneel (verdeeld over 4 kwadranten van fibrotische strictuur). Buiten het zicht en bereik van kinderen houden - Bewaren in de koelkast (2-8°C) in de oorspronkelijke verpakking	
Contactpersoon: [name]. [name], [contact]	
Sponsor: UZ Gent, [name]	

## 7.2.7 Storage conditions

Store in a refrigerator ( $2^{\circ}C - 8^{\circ}C$ ). Do not freeze.

## 7.2.8 Known side effects of the medication

After local injection the collagenases do not reach the bloodstream in significant amounts and are presumed to largely stay at the point of injection until they are broken down by proteases. As a result, side effects are uncommon and are most often injection site reactions including lymphadenopathy (swollen lymph nodes), itching, pain, oedema, and bleeding (for example in the form of bruises or ecchymoses). Allergic reactions are seen in less than 1% of patients Drug accountability

### 7.2.9 Drug accountability

Drug accountability will be documented.

## 7.3 The subjects

### 7.3.1 Number of subjects

Active group: 10 patients presenting with refractory GI strictures.

Control group: A historical cohort that consists of 40 consecutive patients that received an endoscopic balloon dilation 12-15mm for a refractory GI stricture at our centre.

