## 7.3.4 Replacement of subjects

Patients that are not able to participate to the study will receive the standard of care, consisting of endoscopic dilations alone. Only 1 intralaesional administration of the study drug is given at the start of the experiment. Early drop-out of the study (before 6 months) will therefore not impact further standard care of the patient.

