## 8.2 Flowchart

- Between day -7 to day -1: Informed consent

- Day 0: Endoscopy, xiapex injection into the strictures (4 quadrants, 0.75ml or 0.25mg per quadrant)
- Day +1: Endoscopy, CRE balloon dilation 12mm to max 15mm
- Day +2 to month 2: clinical evaluation (by phone) every 2 weeks with a window of 3 days (see above for primary and secondary outcome measures)
- Month 2-month 6: Clinical evaluation (by phone) every 4 weeks with a window of 3 days (see above for primary and secondary outcome measures)

The expected total duration of the trial is 18 months.

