# 9 Randomisation / blinding

Not Applicable, as this is an open label trial.

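### The 40 historical controls must be consecutive but the 10 injected patients need not be, and no screening log is planned, so the choice of whom to approach can bias the comparison in either direction

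*Combined protocol and SAP*

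**What the plan says.** Section 7.1 describes a "Proof of concept open pilot study with a historical control cohort". Section 7.3.1 defines the two groups in adjacent lines. The treated group is "Active group: 10 patients presenting with refractory GI strictures". The control group is "A historical cohort that consists of 40 consecutive patients that received an endoscopic balloon dilation 12-15mm for a refractory GI stricture at our centre". A sampling rule is therefore written for one group only.

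The eligibility criteria narrow the field very little. Section 7.3.2 asks for an adult of up to 90 years, a GI stricture that can be dilated endoscopically, one earlier dilation of it in the preceding 3 months, and signed consent. Section 7.3.3 has a single exclusion, which concerns language. Neither these sections nor Section 8 describes a screening log, a record of refusals or an all-eligible rule. On randomisation and blinding, Section 9 says "Not Applicable, as this is an open label trial".

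Section 3 states a comparative objective against dilation alone. Section 12.3 confirms that outcomes will be compared with the historical group, descriptively, and mentions no matching or adjustment.

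**The concern.** A consecutive series is meant to represent everyone treated at the centre. Ten patients recruited without such a rule represent whoever was approached and agreed. If the clinician tends to offer a new injection to patients who look likely to do well, the treated group will need fewer repeat dilations even if the drug does nothing. If it is offered mainly to the most difficult cases, a real benefit can be hidden.

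Because the analysis is an unadjusted description, any such selection passes directly into the primary outcome, the number of repeat dilations over 6 months. What is at stake is the proof-of-concept reading itself, that is, whether the observed difference encourages or discourages further study. Without a log, a reader cannot tell how many eligible patients were passed over or why.

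**Working it through.** The plan has no figure to reproduce. Section 12.1 says that no sample size was calculated, and 10 and 40 are given without derivation. The check is therefore an illustration of size under stated assumptions.

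**Inputs from the documents:** 10 treated patients, 40 controls, a count of dilations over 6 months, descriptive comparison only.

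**Assumed inputs (none is in the documents):**
- M, the number of eligible patients during accrual: 12, 15 or 20.
- σ, the SD of the log repeat-dilation rate between patients: 0.5 or 0.7.
- ρ, the correlation between the investigator's impression and the true log rate: 0.3 or 0.5.
- No drug effect.

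**Formula.** Let f = 10/M be the share enrolled and q = Φ⁻¹(f). With log-normal rates and a normally distributed impression, the mean rate of the selected patients relative to all eligible patients is, for a large pool:
- easier cases picked: Φ(q − ρσ) / f
- harder cases picked: Φ(q + ρσ) / f

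**Two worked cases.**
- M = 12, σ = 0.5, ρ = 0.3: f = 0.833, q = 0.967, ρσ = 0.15. Easier: Φ(0.817)/0.833 = 0.95. Harder: Φ(1.117)/0.833 = 1.04.
- M = 20, σ = 0.7, ρ = 0.5: f = 0.5, q = 0, ρσ = 0.35. Easier: Φ(−0.35)/0.5 = 0.363/0.5 = 0.73. Harder: Φ(0.35)/0.5 = 0.637/0.5 = 1.27.

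**All cases (easier / harder):**

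| M | σ = 0.5, ρ = 0.3 | σ = 0.5, ρ = 0.5 | σ = 0.7, ρ = 0.3 | σ = 0.7, ρ = 0.5 |
|---|---|---|---|---|
| 12 | 0.95 / 1.04 | 0.92 / 1.07 | 0.93 / 1.06 | 0.88 / 1.09 |
| 15 | 0.92 / 1.08 | 0.86 / 1.13 | 0.88 / 1.11 | 0.80 / 1.17 |
| 20 | 0.88 / 1.12 | 0.80 / 1.20 | 0.83 / 1.17 | 0.73 / 1.27 |

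Simulating pools of exactly 12, 15 or 20 gives slightly milder values, 0.74 to 0.96 and 1.04 to 1.26. Taking both calculations together, the ranges are 0.73 to 0.96 and 1.04 to 1.27. If all eligible patients are enrolled (M = 10), or if the impression carries no information (ρ = 0), the ratio is 1.00.

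**Comparison with chance.** With no selection and no drug effect, an assumed mean of 3 dilations and the same SDs, the observed ratio of 10 to 40 patients has a 95% range of about 0.54 to 1.65 (σ = 0.5) or 0.47 to 1.9 (σ = 0.7). Selection adds to this. In a gamma-Poisson version with mean 3 and frailty variance 0.25, picking the easier 10 of 20 with ρ = 0.3 raises the probability of an observed ratio of 0.70 or less from about 0.12 to 0.21. The 0.70 is only a marker; the plan sets no target.

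**The case against.** **It is a declared pilot.** The protocol says that it is proof of concept with a historical control and plans no test. Discretion over whom to approach is common in such studies. This stands as a reason for a modest tone. It does not remove the point: Section 12.3 concedes that the sample is small, which is a matter of precision, and the groups are still compared.

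**The figures are assumptions, and close to a worst case.** This stands. Pool size, SD and correlation are not documented. The calculation ranks the whole pool at once, whereas patients arrive one by one. The ratio is also to the mean of the eligible pool, so it equals a treated-to-control ratio only if the historical controls resemble that pool. The figures cannot be called comparable to a useful drug effect, because the plan names no effect size.

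**Imbalance might be seen.** This stands in part. The CRF has a medical and surgical history section (Section 11) and the control files are reviewed (Section 8.1), so a gross difference, for example in earlier dilations, could show. An impression not captured in those fields would not.

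A reader might also infer three stronger points, which the documents do not support:
- *That patients are being hand-picked.* The protocol neither permits nor forbids this. It is silent.
- *That data on concurrent patients treated by dilation alone are thrown away.* Section 7.3.4 says: "Patients that are not able to participate to the study will receive the standard of care, consisting of endoscopic dilations alone". That covers those unable to take part, not eligible patients who decline or are never approached, and it says nothing about excluding data.
- *That treated patients are a different kind of case because their dilation is arranged ahead.* The flowchart has "Between day -7 to day -1: Informed consent" and dilation on day +1, which implies at least 2 days from consent to dilation. An inpatient able to wait could still enter. Nothing shows that any control was dilated sooner, or that such patients have a different repeat rate.

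**Conclusion.** The point holds as an asymmetry in Section 7.3.1: consecutive sampling is required of the controls and not of the treated patients, and no screening log is described. With wide eligibility and open treatment, the choice of whom to approach can shift the comparison of repeat dilations either way. Under the stated assumptions the shift is about 4% to 27% in either direction. Its true size and direction cannot be known from the documents, and chance variation with 10 patients is larger. The claim is that selection could distort the result and could not be ruled out afterwards. It is not that selection has occurred or would dominate. The change is worth making because it is cheap and affects who is enrolled, not merely how the study is described.

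**What to change.** In Section 7.3.1, state that consecutive patients who meet Sections 7.3.2 and 7.3.3 will be offered participation until 10 are enrolled. Add that a log will be kept of all patients dilated for a GI stricture during accrual, with the reason for non-entry (ineligible, not approached, declined, other), and that it will be reported with the results.

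The cost is a one-page log and slightly less freedom in whom to approach. The change removes selection by the investigator. It does not remove self-selection through refusal, which the log would at least make visible, or differences in calendar period between the groups.

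Optionally, where consent allows, the 6-month repeat-dilation count of eligible non-participants could be taken from their files and reported. With an eligible pool of 12 to 20 that is only 2 to 10 patients (12 − 10 to 20 − 10), and they are self-selected, so it would be an imprecise concurrent check and not a second comparator. It would also need consent wording for these patients. No restriction on how far ahead the control dilations were scheduled is proposed: no documented problem calls for one, and scheduling times might not be recoverable from old files.

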### 7.3.2 Inclusion criteria

The patient is 18-90 years old The patient suffers from a GI stricture The stricture is amenable for endoscopic dilation The patient has undergone at least 1 previous endoscopic dilation for the same stricture within the last 3 months The patient has signed the ICF

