# 8 Procedures

## 8.1 Procedures

After informed consent, patients with an a refractory upper GI stricture will receive a first esophagogastroscopy or ileocolonoscopy with local injection of XiapexR injection into the stricture prior to dilatation. One vial (0.9mg) xiapex in 3ml dissolvent (also provided by the company) will be divided over 4 quadrants within the fibrotic stricture. After 24 hours, a second esophagogastroscopy or ileocolonoscopy will be performed to perform balloon dilation of the stricture 12-15mm (standard of care). The historical cohort will not undergo any procedures, but their patient file will be reviewed to gain outcome data. ICF will be obtained if the patient is still in follow-up at our department.

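### Controls are selected on a 12-15mm dilation actually received and active patients only on eligibility, so the comparison with the historical cohort may be biased, by an amount and in a direction the protocol does not fix.

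*Combined protocol and SAP*

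**What the plan says.** Section 7.3.1 defines the controls as "40 consecutive patients that received an endoscopic balloon dilation 12-15mm", all treated for a refractory stricture at the study centre. The word consecutive works inside that filter: it orders the patients who had a 12-15mm dilation and brings in no one else. The same section describes the other arm as "Active group: 10 patients presenting with refractory GI strictures".

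The active entry rules are in 7.3.2. The two that bear on dilation are "The stricture is amenable for endoscopic dilation" and "The patient has undergone at least 1 previous endoscopic dilation for the same stricture within the last 3 months". Neither names a balloon size or a stricture diameter.

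For active patients the 12-15mm range appears only as the intended procedure. Section 8.1 places it 24 hours after the injection and calls it standard care. Section 8.2 lists it as "Day +1: Endoscopy, CRE balloon dilation 12mm to max 15mm".

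Section 12.3 plans to compare outcomes with the historical group, descriptively and without adjustment. It defines no analysis set. Section 7.3.4 is headed as dealing with replacement but gives no replacement rule. Nothing says what happens to the data of an injected patient in whom 12mm is not reached, or who has no dilation after the injection.

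**The concern.** The size used at an index dilation is partly a result of the procedure: it depends on how tight the stricture is and how far the operator goes. Section 7.3.1 filters controls on that result. Active patients are enrolled and injected before it is known.

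This matters if tightness at the index procedure is related to later need for dilation or to complications, which is plausible. Section 4 makes the count of repeat dilations over 6 months the primary outcome and the complication rate a secondary one. Section 7.3.6 says that the drug's effect on perforation risk is unknown, so any complication in the active group will be read against these controls. An imbalance in stricture type could then pass for a drug effect, or hide one.

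**Working it through.** There is no figure of the plan's own to reproduce. Section 12.1 gives no sample size calculation, and the protocol states no stricture diameters, dilation counts or complication rates. The check has two parts: a reading of the two selection rules, and an illustration on assumed inputs.

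**1. The rules side by side**

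| | Controls | Active |
|---|---|---|
| Number (7.3.1) | 40 | 10 |
| Selected on | dilation received | eligibility before injection |
| 12-15mm is | a condition of entry | the plan for Day +1 |
| Stricture not reaching 12mm | cannot be included | can be included |
| Stricture dilated above 15mm | cannot be included | a wider stricture can enter, with dilation planned to 15mm at most |

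**2. The two ways of handling an active patient who does not reach 12mm**

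- *Keep the patient.* The active group then holds a type of stricture that the control rule excludes.
- *Drop the patient.* If the injection were inert, this would apply the controls' filter to the active group. But the drug may change who reaches 12mm, or may cause an event that prevents the dilation. Dropping then selects on a result that follows the injection, and can remove the very patients in whom a complication occurred.

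**3. Illustration if such patients are kept and the drug does nothing**

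Let k be the number of tight strictures among the 10 active patients (0 among controls), m the mean number of repeat dilations in other patients, and r the ratio of that mean in tight strictures. All three are assumed.

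Shift in active mean = (k/10) × (r - 1) × m

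- Low end: k = 1, r = 1.25, m = 2 gives 0.1 × 0.25 × 2 = +0.05.
- High end: k = 3, r = 2, m = 3 gives 0.3 × 1 × 3 = +0.9.
- k = 0 gives 0.

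If a share p of eligible strictures is tight, the chance of at least one among 10 is 1 - (1 - p)^10. For p = 5%, 10%, 20% and 30% this is 40%, 65%, 89% and 97%.

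**4. An offset from the entry criteria**

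The listed active criteria ask for one earlier dilation. Controls are labelled refractory, which section 6 defines by failure over three sessions. Assume that a share s of active patients has milder disease with q times the usual count, and m = 3.

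Net shift = 3 × [(k/10)(r - 1) - s(1 - q)]

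- Lowest: k = 1, r = 1.25, s = 0.4, q = 0.5 gives 3 × (0.025 - 0.2) = -0.525, rounded to -0.53.
- Highest: k = 3, r = 2, s = 0.2, q = 0.75 gives 3 × (0.3 - 0.05) = +0.75.

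The sign is not fixed.

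**5. Complications**

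Assume a base perforation risk p0 of 1% to 5% and a ratio R of 2 to 3 in tight strictures. The expected active rate rises by (k/10)(R - 1)p0. That runs from 0.1 × 1 × 1% = 0.1 percentage points to 0.3 × 2 × 5% = 3.0 percentage points. The exact 95% intervals are much wider: 0-30.8% for 0/10, 0.3-44.5% for 1/10 and 0.1-13.2% for 1/40.

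**The case against.** The best reply is that 12-15mm is the standard procedure in both groups, so that limiting controls to it is a matching choice. The wording of 7.3.1 also does not separate the balloon range used from the diameter reached. Active patients must have a dilatable stricture that was dilated in the past 3 months, which may keep out some of the tightest. If every active patient reaches 12-15mm on Day +1 and has strictures like those of the controls, this mechanism adds nothing. The study is also a small pilot with descriptive analysis only, so no test or error rate is affected.

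Much of this stands. It rules out saying that bias has been shown. It does not remove the asymmetry: matching on the planned procedure would be sound, but 7.3.1 matches on the procedure received, and no rule covers an active patient who departs from the plan. A descriptive comparison is still shifted by selection, and none of the planned displays would reveal it.

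Two further points stand. The filter also removes controls dilated above 15mm, which can push the opposite way from tight strictures. Perforation is not a named endpoint; it would fall under complications, where ten active patients cannot separate a shift of the size in step 5 from chance.

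**Conclusion.** The point holds as a possible bias. The selection rules differ as described, nothing elsewhere in the protocol closes the gap, and the outcomes are still to be compared with this cohort.

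A reader might infer more: that the rule does bias both outcomes, or that it makes an inert drug look worse by a definite amount. With 10-30% tight strictures needing 4 rather than 2 repeat dilations, for example, the active mean would be 2(1 - f) + 4f = 2.2 to 2.6 against 2.0, or 10-30% worse. The documents support neither inference. The share and the counts are assumptions, the calculation covers only the tight end, and it leaves out the looser criterion on earlier dilations. The ratio of lumen areas, (15/12)² = 1.56, does not help either, because it compares sizes within a range common to both groups.

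The ranges in the working, +0.05 to +0.9 for this mechanism alone and -0.53 to +0.75 net of milder disease, are illustrations on assumed inputs. They show that a few patients among ten can move the mean visibly and that the direction cannot be told in advance.

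**What to change.** **Section 7.3.1.** Select consecutive historical patients who meet the same pre-procedure eligibility criteria as the active group and in whom balloon dilation of the stricture was attempted. Do not require that 12mm was reached. Keep the same 15mm upper limit as the active group's planned procedure, so that controls treated beyond that range are not brought in.

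**Section 12.3.** Define the active analysis set as every injected patient, whatever size was reached on Day +1 and also if no dilation followed. Extract and report the largest size reached at the index procedure in both groups. Make all patients the main display for the primary count and for complications. Show those who reached 12-15mm as a secondary display only, labelled as conditioning on a post-injection result.

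The changes should be made before control data are extracted. None of them alters what is done to a patient.

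**Cost.** New wording in two sections, one extra item from the endoscopy report, and a slightly more heterogeneous control cohort. Section 8.1 already has the control files reviewed. One limit remains: the 15mm ceiling still filters controls on size at the upper end, so the reported sizes should be read with that in mind.
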